Patients will be asked to rate, using a 0-10mm visual analog scale (VAS), their surgical anxiety level ("On a scale of 0-100, with 0 being not anxious at all to 100 being extremely anxious, how anxious are you about your upcoming surgery?"), their anticipated pain (On a scale of 0-100, with 0 being no pain at all and 100 being pain as bad as you can imagine, how much pain do you anticipate experiencing after your upcoming surgery?"), and using a categorical scale, their anticipated pain medication need ("On a scale of 0 to 5, with 0 being none at all, 1 being much less than average, 2 being less than average, 3 being average, 4 being more than average, and 5 being much more than average, how much pain medication do you anticipate needing after your upcoming surgery?").

Study survey will be administered upon recruitment in antenatal clinic or delivery suite or till 5-14 days after discharge whenever patient is comfortable. It includes Edinburgh Postnatal Depression Scale (EPDS), Pain Catastrophizing Scale (PCS), Central Sensitisation Inventory (CSI), EQ-5D-3L and HADS. The estimated duration of the surveys is about 30 minutes.

Mechanical temporal summation (MTS) assessment using a 180 gram von Frey filament applied to the patient's arm, as demonstrated by Weissman-Fogel, et al.[20], will be done prior to surgery and results recorded. The anesthetic technique will be standardized using the current standards of care. All women will receive antacid prophylaxis with 30 ml sodium citrate. The spinal anesthesia administered will be standardized doses of intrathecal hyperbaric bupivacaine (10.5-12 mg), fentanyl (15 mcg), and preservative-free morphine (100 mcg). Before placing the spinal anesthetic, the skin at the site will be infiltrated with 2-5 ml 1.0% lidocaine as per standard practice. It has been shown that the words used during local anesthetic injection can influence patient's subjective experience of pain, so prior to local anesthetic injection we will use a standardized script to inform patients that local anesthetic is about to be given: "I am now giving you the numbing dose." After the injection is completed and the needle is removed, the anesthesiologist will use a standardized script, "From 0 to 10, where 0 is no pain and 10 is the worst pain imaginable, how much did this procedure hurt?" Patient's responses will be recorded.

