During cesarean delivery: Surgery, intraoperative and postoperative management will be performed according to standard practice. Data will be collected on heart rate, blood pressure, oxygen saturation, presence of nausea and vomiting and use of wound infiltration. Acute pain in the postoperative care unit (PACU) will be treated at clinician's discretion.

After delivery and before discharge from the hospital: The woman is interviewed at 0 to 48 hours on the pain scores at rest and with movement (sitting up in bed from a supine position) and will be recorded in the nursing electronic records. Other data such as nausea scores, and occurrence of vomiting are also noted. Standard routine monitoring of haemodynamics parameters and pain relief will be done in the ward. Study surveys are continued while patient is comfortable before discharge or till 5-14 days after discharge. The survey for post-delivery health status (HADS, EQ-5D-3L) will take about 10 minutes to complete.

Six - Ten weeks after delivery: The patient will have a phone survey/ online survey at 6 -10 weeks post-delivery with: (1) EPDS (2) Pain Survey (3) Pain Vulnerability (PCS, CSI) (4) Breastfeeding Questionnaire (5) EQ-5D-3L and (6) HADS. Patients with scores on the depression scale consistent with postpartum depression will be referred to their obstetrician or primary care physician for further assessment and management.

F9. Please provide details on sample size and power calculation and the means by which data will be analyzed and interpreted (if applicable).

As an observational study, we will target to enrol for up to 200 consented subjects. The primary hypothesis will be assessed with a Pearson correlation test at $\alpha=0.05$ cutoff for statistical significance. The secondary numeric measures of pain, nausea, and satisfaction will be assessed for correlation with the preoperative measures using a Pearson correlation test. Anticipating that some patients will not require rescue oxycodone, we plan to analyze the time to rescue oxycodone via Kaplan-Meier mean time to event analysis. Dichotomous variables will be assessed via chi-square tests or fisher exact tests.

F10. List all activities that are carried out as part of research in this study. Please state/list all procedures involved in this research study and attach the data collection form (if any) which will be used for CIRB review.

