The duration of study period for each participant can last about 17 weeks. Below are the main time points for the study activities:

Before surgery (duration: 4 weeks):

- Patient screening and recruitment before the surgery: gestational age week 36 and above
- Baseline Demographic data collection
- Survey and data collection (EPDS, pain score, vital signs, HADS score, EQ-5D-3L, MTS, "three questions", pain vulnerability (PCS, CSI))

After surgery (duration of labour till 5-14 days after discharge: ~19 days):

- Pain assessment, survey and data collection (pain score, vital signs, HADS score, EQ-5D-3L, analgesia usage, occurrence of vomiting, and nausea scores)

Follow up phone call survey at 6 - 10 weeks after delivery (duration: 10 weeks):

- Phone survey/ Online survey and data collection (EPDS, breastfeeding, HADS score, EQ-5D-3L, pain score, and pain vulnerability (PCS, CSI))

F11. Please describe the participant's visits (frequency and procedures involved). For studies with multiple visits, please attach study schedule.

There will be 3 visits in total. The duration of study period for each participant can last about 17 weeks. Below are the main time points for the study activities:

Visit 1-Before surgery (duration: 4 weeks):

- Patient screening and recruitment before the surgery: gestational age week 36 and above
- Baseline Demographic data collection
- Survey and data collection (EPDS, pain score, vital signs, HADS score, EQ-5D-3L, MTS, "three questions", pain vulnerability (PCS, CSI))

Visit 2-After surgery (duration of labour till 5-14 days after discharge: ~19 days):

- Pain assessment, survey and data collection (pain score, vital signs, HADS score, EQ-5D-3L, analgesia usage, occurrence of vomiting, and nausea scores)

Visit 3-Follow up phone call survey at 6 - 10 weeks after delivery (duration: 10 weeks):

- Phone survey/ Online survey and data collection (EPDS, breastfeeding, HADS score, EQ-5D-3L, pain score, and pain vulnerability (PCS, CSI))

F12. Discuss the potential difficulties and limitations of the proposed procedures and alternative approaches to achieve the aims.

There will be drop out in the follow up phone survey. However, the withdrawal rate has been accounted for.

F13. What are the potential risks to participants?

During the MTS pain assessment, a test would involve the repeated sensation of pinprick testing for increased sensitivity of pain to pinprick in some individuals.

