Analgesic choices will be made upon patient request and routine hospital protocol, monitoring and recording will apply. If subjects are screened to have high EPDS (13 or more) or persistent pain, they would be advised to seek clinical psychiatric or pain assessment at KK Hospital. The assessment would be done as clinical work and not research funded.

No new research medications are involved by joining the study. The drugs being delivered are the same as what the patient shall receive as standard care.

F14. What are the potential benefits (direct as well as indirect) to participants? Indirect benefit may refer to the medical knowledge gained in the future, from the research.

As this will be an observational study, there will be no direct benefits or harms to patients who choose to participate in this study. On a population level, the data collected in this study may help to improve pain management for women undergoing cesarean delivery in the future.

F15. What is the estimated timeline for this study?

(i) Estimated start date 01-Jun-2017

(ii) Estimated end date 01-Jun-2019

Section G: Recruitment Details

G1. How will potential participants be identified? Please tick all the applicable boxes.

NOTES:

If you have selected that participants are “Patients of study team”, please select “Yes” for K6. If healthy volunteers are recruited for the study, please select the option “Other methods of participant identification” and describe your method(s) of participant identification.

- Referral by attending healthcare professional
- Patients of study team
- Databases
- Other methods of participant identification

G2. Who will make the first contact with participant?

Investigators and the clinical research coordinators in the study team will make the first contact with participant.

G3. How will the participant be contacted?

This study will be advertised with brochures. These will be distributed through KKH, and given to all patients who meet the inclusion criteria during antenatal period. Potential study patients may be invited to participate by study team members in the antenatal clinics/wards and preoperative rooms/wards at KKH. On admission to preoperative rooms/wards, they will again be given a study brochure. The investigators and study team will be available to answer any queries on this trial in the antenatal clinics/wards and preoperative rooms/wards, through phone and email correspondence.

Recruitment of patients from antenatal clinics/wards:

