For the 6-10 weeks online survey, participants' confidentiality will be protected as the online survey link will be sent to their email address only. No names or identification number that will identify subjects will be available on the online surveys and in the system. Only the Principal Investigator and designated Clinical Research Coordinator will have the access to the online surveys by using the designated secured password protected survey monkey login account.

iii. Are there any other measures in place to protect the confidentiality of the research data?

For electronic database REDCap, No names or identification number that will identify subjects will be ensured. The subjects are only identified by study number.

For online survey, No names or identification number that will identify subjects will be available on the online survey and in the system.

iv. Are there any research data sharing agreements with individuals or entities outside the Institution, to release and share research data collected?

No

v. Describe what will happen to the research data when the study is completed.

The research data will be kept under lock and key and using computer security of Singhealth. The data will be destroyed after keeping for 6 years upon completion of the study.

K2. Will any part of the study procedures be recorded on audiotape, film/video, or other electronic medium?

No

Section L: Data & Safety Monitoring

L1. The purpose of the Data and Safety Monitoring Plan is to ensure the safety and well-being of participants, and the integrity of the data collected for the study. Depending on the type and risk level of the study, this may include the Principal Investigator, experts within the department or institution, independent consultants or a combination of the said persons.

Who will perform the data and safety monitoring?

The data is kept by the principal investigator under lock and key and using computer security of SingHealth. The data is accessible only by the investigators for analysis purposes only. The plan for adverse effect monitoring would include reporting to Health Science Authority and CIRB.

L2. Please describe the frequency of review (e.g. daily, weekly, quarterly) and what data (e.g. adverse events/serious adverse events) will be monitored for safety.

Safety data is monitored at all times by the investigators. There will be monthly meeting to review the trial.

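### Do F8 and F13 give conflicting instructions for a high EPDS score at 6-10 weeks after delivery?

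*Protocol*

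**What the plan says.** The EPDS is part of the last contact. F8 says "The patient will have a phone survey/ online survey at 6 -10 weeks post-delivery with: (1) EPDS", and the Visit 3 list in F10 and F11 agrees: "Phone survey/ Online survey and data collection (EPDS, breastfeeding, HADS score, EQ-5D-3L, pain score". It is also a baseline item. The pre-surgery list begins "Survey and data collection (EPDS, pain score, vital signs, HADS score, EQ-5D-3L, MTS", and F8 allows the survey that contains it to be completed at recruitment or as late as 5-14 days after discharge.

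Two sections say what happens to a woman with a high score:

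- F8, under the 6-10-week heading: "Patients with scores on the depression scale consistent with postpartum depression will be referred to their obstetrician or primary care physician". No number is given.
- F13, under risks to participants: women with "high EPDS (13 or more) or persistent pain, they would be advised to seek clinical psychiatric or pain assessment at KK Hospital". No time point is given, and the assessment is described as clinical work outside the research budget.

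On the online version of the survey, K1 says "Only the Principal Investigator and designated Clinical Research Coordinator will have the access to the online surveys". Of the REDCap database it says "The subjects are only identified by study number".

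**The concern.** Set next to each other, the sections differ in three respects for the same 6-10-week score: who acts (the study refers, or the woman is advised to seek care), where she is directed (obstetrician or primary care physician, or psychiatric assessment at the study hospital), and what sets it off (no number, or 13 or more). Neither section cites the other, and nothing elsewhere says whether one replaces the other or both apply.

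This is an instruction about participant safety. A coordinator who worked only from F8 would have no threshold. One who worked only from F13 might give advice and make no referral. Identical scores could then be handled differently. For online responses there is the further question of whether a high score can be traced to the woman at all.

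**Working it through.** No arithmetic applies. The check compares the texts in four steps.

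**1. Which instruction covers which EPDS score?**

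| When the EPDS is completed | F8 instruction | F13 instruction |
|---|---|---|
| At recruitment, before surgery | no | yes |
| First survey delayed, up to 5-14 days after discharge | no | yes |
| 6-10 weeks after delivery | yes | yes |

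F13 has no time limit and so covers every row. The two overlap only in the last row. No EPDS score is left without an instruction. The middle row matters because the visit lists alone would suggest that the EPDS is taken only before surgery and at 6-10 weeks, whereas F8 lets the first survey run on after delivery.

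**2. Can both be followed in the last row?** Take each element in turn.

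- *Action.* Making a referral and giving advice can both be done for the same woman.
- *Recipient.* Neither section says that its route is the only one.
- *Trigger.* One section gives 13 or more and the other gives no number. A stated number and a missing number do not conflict.

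**3. What if staff read F8's unnumbered trigger in some other way?** Let F8 be applied at a threshold t.

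- If t = 13, both sections apply to the same women.
- If t is below 13, women scoring from t to 12 are referred under F8 as well. Nobody at 13 or more is lost.
- If t is above 13, women scoring from 13 up to t are still advised under F13.
- If F8's depression scale were read as the HADS, which is in the same survey, F8 would act on that score, and F13 would still apply to the EPDS.

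In every case a woman with an EPDS of 13 or more is directed to clinical assessment by at least one section.

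**4. Can the difference reach an analysis?** The primary analysis in F9 is a Pearson correlation for the primary hypothesis, which relates pain on local anaesthetic injection to post-cesarean pain. Pain scores at rest and on movement are taken at 0 to 48 hours (F8). The 6-10-week survey comes later and is the last of the three visits, so any action on its EPDS follows the last measurement in this study. A response to an earlier EPDS could in principle influence the 6-10-week EPDS, but earlier scores fall under F13 alone, so the difference in wording plays no part there.

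**Online responses.** K1 excludes names and identifying numbers from the online survey. It does not exclude the study number that REDCap already uses, and it gives two named roles access to the responses. No misstatement is shown there.

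**The case for a change.** The best case for acting is that a safety instruction should be stated once. Whether the study makes the referral or leaves the woman to seek care decides who is responsible for seeing it through. Borrowing the number in F13 settles only the trigger and leaves action and recipient open. Nor is this something to leave to a statistical analysis plan, since the protocol has already addressed it in two places. High scores are foreseeable: F3 links severe acute pain to postpartum depression, and F1 lists that condition as a secondary outcome.

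Much of this stands. The wording differs, the link is missing, and a reader has to combine the two sections. What does not stand is the step to divergent handling. It assumes that staff follow one section of a single form and disregard the other. F8 answers a question about procedures and F13 one about risks. Both are current text, and complying with the form means complying with both. Even someone who used only one section would still direct a woman they judged to have a high score to clinical assessment.

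**Conclusion.** The concern identifies a real difference in wording but not a fault that calls for a change to the plan. The two instructions are compatible, together they cover every EPDS completion, and no estimate, test or sample size depends on them. What is left is an unstated detail, namely that both apply, which the study team can supply by reading the sections together. Linking them would be a reasonable tidying step if the form were being amended for another reason.

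The conclusion rests on two assumptions: that both sections are in force for the same staff, and that the depression scale in F8 is the EPDS, the natural reading given its reference to postpartum depression. If the second fails, the conclusion still holds, as step 3 shows. The number of women concerned cannot be given. The pilot figure in F5, 62 of 479 (12.9%), is a psychiatrist's diagnosis and not a rate of EPDS scores of 13 or more. No view is taken here on which route or cut-off is right.

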E4. Who will be responsible for research-related costs? For sponsored studies, please list the costs that will be borne by the sponsor.

Anaesthesiology ACP Pilot Research Grant

Section F: Research Methodology

F1. Please provide an abstract of your proposed research (Up to 300 words).

Approximately 1 in 5 women who undergo cesarean delivery would suffer from severe post-operative pain, which may further increase their risks from developing postpartum depression. Predictive factors such as pre-operative pain, age and anxiety could significantly contribute to post-operative nausea and vomiting (PONV) and pain in general surgery, however little information is available with regards to cesarean delivery. Previous studies demonstrated that pain scores upon local anesthetic injection is positively correlated to post-cesarean pain scores. Additionally, anxiety, anticipated post-operative pain score and anticipated medication need are also found to be promising risk factors to postcesarean pain management.

We aim to investigate the risk factors of causing post-operative emesis after cesarean delivery, and to reaffirm that there is a positive correlation between pain on local anesthetic injection, presence of mechanical temporal summation (MTS) and post-Cesarean pain scores. We will recruit 200 parturients undergoing cesarean delivery at KK Women's and Children's Hospital and requiring regional anesthesia. Pain and anxiety assessment will be conducted via visual analogue scoring (VAS), MTS assessment and a series of questionnaires. After the delivery, all patients will be given appropriate analgesia, and the pain score at movement will be recorded. Secondary outcomes include pain scores at rest, analgesia consumption, time-to-first-rescue analgesia, opioid-related side effects, patient satisfaction and postpartum depression.

This proposal will determine the clinical relevance of pre-operative determinants for post-cesarean pain management in local context. This would help us discover new risk management strategies and identify modifiable treatment. We hope that this will serve as a guideline for consistent and reliable delivery of care while enhancing the effectiveness and patient satisfaction in obstetrics pain management.

F2. What are the specific aims and hypothesis of this study?

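### F9 expects women who never need rescue oxycodone, yet summarises time to rescue by a Kaplan-Meier mean with no time limit, so the mean is not identified

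*Protocol*

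**What the plan says.** The protocol's abstract (F1) lists the outcome among the secondary ones: "Secondary outcomes include pain scores at rest, analgesia consumption, time-to-first-rescue analgesia". None of the aims or hypotheses in F2 refers to it. F9 gives its analysis in one sentence. It opens "Anticipating that some patients will not require rescue oxycodone" and continues "we plan to analyze the time to rescue oxycodone via Kaplan-Meier mean time to event analysis". F9 states no time limit for that mean, and no other section supplies one.

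Two periods elsewhere could be taken for a limit:

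- F8, after delivery: "The woman is interviewed at 0 to 48 hours on the pain scores at rest and with movement". This window belongs to the pain scores. The same paragraph adds "Standard routine monitoring of haemodynamics parameters and pain relief will be done in the ward", with no end time of its own.
- F10 and F11 head the second block of study activities "After surgery (duration of labour till 5-14 days after discharge: ~19 days", and the item under that heading is "Pain assessment, survey and data collection (pain score, vital signs, HADS score, EQ-5D-3L, analgesia usage, occurrence of vomiting, and nausea scores". Analgesia usage therefore falls in a collection period of about 19 days, with no separate cut-off.

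**The concern.** Choosing Kaplan-Meier because some women will have no event is sound. The difficulty is the summary taken from the curve. A mean needs the whole curve down to zero, and F9 itself expects that the curve will not get there. Software will still print a mean, but it is the area up to some time: a horizon the analyst sets, the last rescue, or the last observed time.

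Two analysts following F9 faithfully could report quite different means from the same women. Neither figure could be set beside another study's unless both used and reported the same cut-off.

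**Working it through.** The protocol gives no rescue rate, mean time or horizon for this outcome, so there is no planned figure to reproduce. The check has three steps.

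**1. Is the mean identified?** Let S(t) be the proportion not yet rescued at time t, and p the share never rescued. The mean is the integral of S(t) from 0 to infinity. Since S(t) ≥ p at all times, the area up to time T is at least p × T, which has no limit as T grows. This needs only p > 0, which F9 expects. It assumes nothing about the shape of the curve.

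**2. How much does the cut-off matter, whatever the distribution?** Moving the horizon from T1 to T2 adds the integral of S(t) between them, which is at least p × (T2 − T1). The protocol's two windows are 48 h and 19 × 24 = 456 h, a gap of 408 h. The least possible increase is therefore:

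- p = 10%: 0.1 × 408 = 40.8 h
- p = 30%: 0.3 × 408 = 122.4 h
- p = 50%: 0.5 × 408 = 204.0 h

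**3. Illustration.** Assume an exponential time to rescue with mean m among women who are rescued. The area to T is p × T + (1 − p) × m × (1 − exp(−T/m)). With p = 0.3 and m = 12 h:

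- T = 48 h: 14.4 + 8.4 × (1 − exp(−4)) = 14.4 + 8.25 = 22.6 h
- T = 456 h: 136.8 + 8.4 = 145.2 h, about 6.4 times as large

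Over a range of assumed inputs:

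| Share never rescued | m = 12 h: to 48 h | m = 12 h: to 19 days | m = 24 h: to 48 h | m = 24 h: to 19 days |
|---|---|---|---|---|
| 10% | 15.4 h | 56.4 h | 23.5 h | 67.2 h |
| 30% | 22.6 h | 145.2 h | 28.9 h | 153.6 h |
| 50% | 29.9 h | 234.0 h | 34.4 h | 240.0 h |

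Convention alone also moves the figure. In 500 simulated samples of 200 women (p = 30%, m = 12 h, end of observation assumed uniform between 48 and 96 h), the average Kaplan-Meier mean was 22.6 h cut at 48 h, 25.7 h cut at the last rescue, and 36.9 h cut at the last observed time. The spread of observation times is an assumption with no source in the protocol, so these three values show the mechanism, not its size in this study.

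**The case against.** The strongest reply is that a truncation time and a censoring rule are normally left to the statistical analysis plan, which is not at hand. F9 does not call the mean unrestricted, and any Kaplan-Meier mean from censored data is an area to some time, so F9 can be read as a restricted mean whose limit is still to be given. Part of this stands. An analysis plan could repair the point in a line, and the proposed change keeps the same curve. But F9 does more than leave a detail open: it names the mean in the very sentence that states the condition under which that mean is not identified.

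It can also be said that 48 h is implied. It is a natural candidate, but the text attaches it to pain scores, and F10 and F11 place analgesia usage under a much longer period.

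The numerical inputs are assumed, and that objection stands in full. The illustration shows how strongly the mean depends on its limit, not the error this study would make.

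Three stronger readings are tempting, and the protocol supports none of them:

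- A reader might infer that the cut-off will fall to length of hospital stay. The collection period in F10 and F11 runs past discharge, so this is not established.
- A reader might infer that F1 and F9 define different events, because F1 speaks of rescue analgesia and F9 of oxycodone. A general label in an abstract followed by a more specific methods sentence is not a contradiction.
- A reader might conclude that Kaplan-Meier is the wrong method. It suits the censoring; only the mean without a limit fails.

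**Conclusion.** The point holds, as a minor one. F9 names a mean that is not identified under its own expectation, and the protocol offers two possible limits without tying either to rescue. That conclusion rests only on some women never being rescued.

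The distribution-free size is at least the never-rescued share of an hour for each extra hour of horizon. The figures of 22.6 h and 145.2 h depend on the assumed 30% and 12 h.

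A reader might infer that the study's main result is at risk. It is not: the primary Pearson correlation and the target of 200 women do not depend on this outcome, and no stated aim does either.

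**What to change.** In F9, replace the Kaplan-Meier mean with the restricted mean time to rescue oxycodone up to one pre-stated horizon over which rescue use is recorded for all women. The 48 h that matches the pain interviews is one example. Report beside it the Kaplan-Meier proportion rescued by that time, which shows directly how many women needed no rescue within the horizon. A median would be a weaker substitute, since it can be estimated only if at least half the women are rescued. If the analysis plan already states a horizon, F9 should be brought into line with it.

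The cost is about two lines of text. Analgesia usage is already collected, and the planned analysis already needs the time of first rescue, so no extra patients or procedures follow.

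There are two downsides. The result is specific to the chosen horizon. And if any women leave hospital before it and are censored at discharge, that censoring may be informative, because women with less pain may leave earlier. The number censored in this way should be reported.

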Ultimately, this trial will lay a strong foundation for subsequent prospective randomized clinical trials to determine whether rigorous risk stratification, psychological treatment and analgesic interventions can prevent PONV and improve pain after childbirth. This proposal will also be the basis of framework for future research in pain and related psychological disorders. Foreseeable applications may include functional brain imaging extending the capabilities of the NMRC Transition Award which is still being developed. Future research studies, based on the model, drug interventions, targets and psychological interventions would lead to better healthcare and patient outcomes.

F8. Discuss in detail the experimental design and procedures to be used to accomplish the specific aims of the study. If this study involves a retrospective medical record review, please specify the period of data collection.

The proposed study is an observational study in 200 women who undergo cesarean delivery at KK Women's and Children's Hospital, Singapore. Informed consent will be obtained from all subjects. Singhealth Centralised Institutional Review Board approval and Clinical Trials Registration will be obtained.

Before delivery

Women scheduled to undergo a cesarean delivery under spinal or combined spinal epidural anesthesia will be approached to participate in the study. After obtaining informed consent, patients will be asked about any history of PONV after CD, history of PONV after non obstetric surgery, history of morning sickness, history of hyperemesis gravidarum, history of

motion sickness, smoking history, and occurrence of intraoperative nausea and vomiting. The obtained data will be documented in Data Collection Form.

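### F9 analyses time to rescue only by a Kaplan-Meier mean with no predictor or comparison, so as written this secondary outcome says nothing about prediction

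*Protocol*

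**What the plan says.** The abstract (F1) lists the outcome: "Secondary outcomes include pain scores at rest, analgesia consumption, time-to-first-rescue analgesia, opioid-related side effects, patient satisfaction and postpartum depression". Section F9 gives the analyses, and three of its statements matter here.

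- Numeric outcomes: "The secondary numeric measures of pain, nausea, and satisfaction will be assessed for correlation with the preoperative measures using a Pearson correlation test".
- Time to rescue: "Anticipating that some patients will not require rescue oxycodone", the protocol continues, "we plan to analyze the time to rescue oxycodone via Kaplan-Meier mean time to event analysis".
- Binary outcomes: "Dichotomous variables will be assessed via chi-square tests or fisher exact tests".

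On design, F8 states: "The proposed study is an observational study in 200 women who undergo cesarean delivery". There are no arms. The predictors in F2 and F8 are injection pain (0 to 10), surgical anxiety and anticipated pain (each 0 to 100), anticipated medication need (0 to 5) and MTS, for which secondary hypothesis (1) in F2 uses MTS>0. F2 frames every hypothesis and its aim, apart from the exploratory emesis aim, around post-cesarean pain. I take the rescue oxycodone of F9 to be the time-to-first-rescue outcome of F1.

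**The concern.** F3 gives the study's purpose as evaluating preoperative measures for predicting postoperative pain. A secondary outcome earns its place in such a study by being related to those measures. F9 does this for numeric pain, nausea and satisfaction, but time to rescue receives a method with no predictor in it. In a trial with arms, a Kaplan-Meier analysis carries an implicit comparison between them. Here no arms exist to supply one.

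If F9 is followed literally, the outcome is reported as an average time for the cohort and nothing is learned about who needs rescue earlier. If analysts see the gap after the data are in, they may split the scores to get curves to compare. The choice of cut would then be open.

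**Working it through.** **1. Does any statement in F9 link time to rescue to a predictor?**

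| Outcome type in F9 | Method | Linked to preoperative measures? |
|---|---|---|
| Numeric pain, nausea, satisfaction | Pearson correlation | Yes, stated |
| Time to rescue oxycodone | Kaplan-Meier mean | Not stated |
| Dichotomous variables | Chi-square or Fisher | Not stated; does not cover a censored time |

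No other section of the protocol makes the link.

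**2. The plan's own figure.** The target of 200 comes with no effect size, power or rescue rate, so there is nothing to reproduce.

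**3. What a pooled Kaplan-Meier mean can show.** The mean is the area under the estimated curve up to a horizon. It uses rescue times and censoring and no covariate. As a check, cohorts of 200 were simulated with an injection-pain-like score (mean 4, SD 2, limited to 0 to 10), a log hazard rising 0.4 per SD, and follow-up to 48 h. All of these are assumptions. The score was then shuffled among the women.

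| Rescues | KM mean, real / shuffled | Cox HR per SD, real | Cox HR per SD, shuffled |
|---|---|---|---|
| 48 | 41.8 h / 41.8 h | 1.47 (p=0.018) | 0.89 (p=0.48) |
| 77 | 37.6 h / 37.6 h | 1.33 (p=0.014) | 1.16 (p=0.23) |
| 108 | 33.7 h / 33.7 h | 1.68 (p<0.001) | 1.20 (p=0.09) |

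The mean is identical by construction. In these cohorts Cox regression separates the two cases.

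**4. Dependence on the horizon.** When some women are never rescued, the mean depends on where the curve is cut off. In the 77-rescue cohort it is 37.6 h at 48 h and 21.3 h at 24 h. F9 states no horizon. The 0 to 48 hours in F8 is given for pain scores.

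**5. What the data could support with a predictor in the model.** For a standardised score in a Cox model, with D rescues, two-sided 0.05 and 80% power, the detectable hazard ratio per SD is exp[(1.96 + 0.84)/√D].

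| Assumed rescued | D | Detectable HR per SD |
|---|---|---|
| 20% | 40 | exp(2.80/6.32) = 1.56 |
| 40% | 80 | exp(2.80/8.94) = 1.37 |
| 60% | 120 | exp(2.80/10.95) = 1.29 |
| 80% | 160 | exp(2.80/12.65) = 1.25 |

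For MTS>0, with an assumed prevalence of 20% to 50% and an assumed hazard ratio of 2.0, Schoenfeld's formula gives power of 42% to 59% at 40 rescues, 70% to 87% at 80, and 86% to 97% at 120.

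**6. Illustration only: an improvised median split.** For a normal score the halves differ by 2√(2/π) = 1.596 SD, so the test statistic shrinks by 1.596 × √0.25 = 0.798. Efficiency is 0.798² = 2/π = 64%, like losing 200 × 0.36, about 73 women. Power of 80% becomes Φ(0.798 × 2.80 − 1.96) = 61%. F9 proposes no such split.

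**The case against.** The strongest reply is that F9 is a short box in an ethics form and never says the mean is pooled. The preceding sentence sets the purpose, correlation with the preoperative measures. The rescue sentence may change only the method, because some times are censored. Covariates for a secondary survival analysis are often left to a statistical analysis plan, and one may exist. The first part is a fair reading of intent. But F9 is not silent: it commits to a specific method, and that method, taken as stated, has no place for a predictor. A later plan would have to add to it.

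Three stronger inferences are tempting, and the reply is right to resist them.

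- A reader might infer that Kaplan-Meier methods cannot address prediction here. They can: MTS>0 in F2 is a ready two-group split, and anticipated medication need already has six labelled levels. F9 does not tie either to time to rescue, and it sets no cut for the other scores.
- A reader might infer that the study's hypotheses go untested. They do not: F2 concerns post-cesarean pain, and the Pearson analyses are untouched.
- A reader might take the fall from 80% to 61% power as a property of the plan. It describes a split that the protocol never proposes, and it assumes a normal score.

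It is also fair that several Cox models add several estimates, and that the simulation in step 3 confirms only that a pooled mean ignores covariates.

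**Conclusion.** The point holds in limited form. As written, F9 yields no information on the association between any preoperative measure and time to rescue. This concerns one listed secondary outcome, so it is a change that should be made and not a threat to the primary analysis.

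The conclusion rests on the wording of F9 and the single-cohort design, and it needs no numerical assumption. The detectable hazard ratios do rest on assumptions: the rescue proportion, the MTS prevalence and the hazard ratio for MTS are not in the protocol. They show that a predictor model would be informative for moderate associations if rescue is common, and weak if few women are rescued.

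**What to change.** In F9, state that time to first rescue will be related to each preoperative measure by Cox regression. Enter injection pain, anxiety, anticipated pain and anticipated medication need as scores, and MTS either as MTS>0 or as a score, chosen in advance. Report hazard ratios with 95% CI as secondary results. State the time origin and one fixed horizon at which women without rescue are censored. Keep Kaplan-Meier curves, for example by MTS>0, as description.

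The cost is analysis wording. F10 already lists analgesia usage among the data collected, though the time of first rescue must be captured from those records. The downsides are a proportional-hazards check and several secondary estimates, which should be read as supportive and not as separate tests of the F2 hypotheses.
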